2.3. Selection criteria

Participants must meet all the following eligibility criteria:

- Seeking care from primary health-care practice or a specialised outpatient hospital facility (DK) for non-specific LBP within the past 8 weeks
- LBP of any duration
- Mild-to severe pain-related disability rated as 6 or above on the Roland Morris Disability Questionnaire (RMDQ)
- Age ≥ 18 years
- Own and regularly use a smart phone (with at least Android 6.0+ or iOS11.0+) with internet access (Wi-Fi and/or mobile data)
- Have a working email address and have access to a computer with internet access to complete questionnaires in a web browser.

Presence of any of the following criteria will exclude participants from enrolling in the RCT:

- Not interested
- Unable to speak, read or write in the national language (Danish/ Norwegian)
- Cognitive impairment or learning disabilities
- Mental or physical disease or health problem limiting participation in the study (Examples are fractures or pathologies, such as cancer, inflammatory diseases, and signs of radiculopathy (severe leg pain, loss of leg strength, or loss of or altered sensation in a myotomal or dermatomal distribution))
- Unable to take part in exercise/physical activity (such as non-ambulatory patients, use of walking aids/assistance, unable to get down and up from the floor independently)
- Fibromyalgia (diagnosed by a health care professional (HCP))

- Pregnancy
- Previous back surgery
- Ongoing participation in other research trials for LBP management.

The assessment of whether the criteria are considered to limit participation is performed either by the referring HCP during the recruitment phase (see green box in **Figure 1**) or by participant self-report during the screening call (see blue box in **Figure 1**).

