5.1. Sample size estimations

The study is designed as a superiority trial with two parallel groups, selfBACK in addition to usual care versus usual care only. We hypothesis that the intervention group (selfBACK in addition to usual care) will have a two-point difference in pain related disability (RMDQ) compared to the control group (usual care) at three months follow-up. The sample size calculations have been performed in two ways. First, we conducted a simple calculation assuming only one follow-up measure and a standard deviation (SD) of the RMDQ score of six points. The expected SD was informed by previous high-quality studies in DK and UK investigating similar LBP populations [67-70]. Based on these calculations we estimated that a sample size of 382 (191 in each group) was necessary to detect a two-point difference with 90% power and a two-sided alpha level of 0.05.

We then performed a simulation using 1000 repetitions of a mixed model regression for repeated measures, assuming 1) three data points per participant (i.e. baseline, six weeks and, three months), 2) an effect of treatment of two points, 3) a SD of six points, and 4) a correlation between repeated measures of 0.4. The latter was based on information from previous trials with repeated measures for the RMDQ in similar LBP populations [71, 72]. As in the simple calculations reported above, we used an alpha level of 0.05. Based on these assumptions, sample size calculations showed that 250 participants (i.e. 125 participants in each group) give a power of 92% (95% confidence interval [CI 90-93]) to detect a two-point difference in RMDQ between study groups at three months. Furthermore, simulations assuming a two-point difference between groups at both six weeks and three months indicated that a sample size of 180 (90 in each group) give a power of 94% (95% CI, 92-95). Taken together, these sample size calculations indicate that a sample size of ~250 persons (125 in each group) will be sufficient under the given assumptions if the statistical analyses utilise the repeated measure design. A recent systematic review showed that attrition rates ranged between 4-94% for digital self-management interventions lasting between two weeks and 12 months in LBP populations [25]. To allow for a 30%

drop out rate at three months follow-up we aim at including a total of 350 participants in the trial; 175 participants in each arm.

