5.2. Statistical analysis

The primary analysis will estimate the mean difference with a 95% confidence interval (CI) in RMDQ score at three months follow-up between groups (selfBACK in addition to usual care versus usual care only). The analyses will be conducted according to the intention-to-treat principle using a linear mixed model for repeated measures. This model includes all available data for all participants at each time point (i.e. baseline, six weeks, and three months). In the regression model, individual participants will be specified as a random effect, accounting for the within subject covariance structure. The effect of group and time will be specified as fixed effects using a joint variable of intervention and time. Here, baseline levels are pooled over the two study groups assuming that any baseline differences are due to chance [73]; this also controls for any baseline differences in the outcome variable. The analysis will investigate the effect of the intervention as constant over time, as well as an interaction between time and group allocation. The between group difference will be estimated both in a crude model, and adjusted for the two variables used for stratification in the randomisation i.e. country and care provider [74]. Further adjustment for baseline levels of other prognostic factors will be considered.

Any missing values are inherently accounted for in the mixed model approach [75], but multiple imputation methods and complete case analysis will be applied in sensitivity analyses. Possible modifiers of the effect of intervention on the primary outcome will be assessed in supplementary analyses stratified by gender, age groups, socioeconomic status and different levels of LBP severity etc., and accompanied by tests of statistical interaction.

Secondary outcomes will be analysed using a similar approach as described above for the primary outcome, with linear mixed models for repeated measures. Analyses of data from six- and nine-months follow-up will also be analysed according to the above description for the primary outcome. The precision of the estimates from the statistical analyses will be assessed by 95% CI.

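### Age and LBP severity are assessed as effect modifiers in groups, which loses power against continuous interactions; if severity means baseline RMDQ, a random-intercept fit within strata also inflates false positives

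*Protocol*

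**What the plan says.** Section 5.2 (Statistical analysis) of the protocol looks for modifiers of the effect on the primary outcome in "supplementary analyses stratified by gender, age groups, socioeconomic status and different levels of LBP severity etc., and accompanied by tests of statistical interaction". It gives no cut-points, no number of groups, no definition of LBP severity, no form for the interaction term and no separate model.

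The only model described is the primary one. Baseline RMDQ is one of its responses: "This model includes all available data for all participants at each time point (i.e. baseline, six weeks, and three months". Its mean is common to both arms: "baseline levels are pooled over the two study groups assuming that any baseline differences are due to chance". On the covariance the text says only that "individual participants will be specified as a random effect, accounting for the within subject covariance structure".

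Two scales could carry severity. Section 2.3 grades disability on the RMDQ: "Mild-to severe pain-related disability rated as 6 or above on the Roland Morris Disability Questionnaire (RMDQ". Section 4.2 records average and worst pain intensity from 0 to 10. The SAP supplied covers the cost-effectiveness analysis only. Its Section 1 says that a main-trial SAP exists, but that document is not available here.

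**The concern.** Two things are at stake.

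- **Power.** Cutting a quantitative modifier into groups discards the variation within groups. Interaction tests are already weak in a trial sized for a main effect, so an avoidable loss matters.
- **Type I error.** If participants are split on baseline RMDQ while it is still a response, its variance within each stratum shrinks, as do its covariances with the follow-up scores. A random intercept assumes equal variances and equal covariances over the three visits. It then understates the variance of the three-month score, and the standard error of the three-month effect comes out too small.

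The intervention is individually tailored, so readers will look to these analyses for who benefits.

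**Working it through.** **Inputs from the protocol.** Section 5.1: difference of 2 points, "a standard deviation (SD) of the RMDQ score of six points", correlation 0.4, "with 90% power and a two-sided alpha level of 0.05", 350 enrolled, 30% drop-out at three months. Section 2.3: entry at RMDQ 6 or above. Section 4.1: range 0-24.

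**1. The plan's own figure.** Per arm, 2 × 36 × (1.960 + 1.282)² / 2² = 18 × 10.51 = 189.1, so 190. The t-based solution is 190.1, rounded up to 191, or 382 in total. The stated 382 reproduces.

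**2. Information kept by grouping.** For a linear modifier this is the between-group share of its variance.

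| Grouping | Normal | RMDQ-like (limited to 6-24) | Uniform |
|---|---|---|---|
| Median split, loss | 1 − 2/π = 36% | 31-34% | 1/4 = 25% |
| Three equal groups, loss | 21% | 15-18% | 1/9 = 11% |
| Four equal groups, loss | 14% | 9-11% | 6% |

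An uneven 25/75 split loses 35-57%, depending on shape.

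**3. From information to power.** A two-sided 5% test with 80% power has an expected z of 1.960 + 0.842 = 2.80.
- Median split, normal modifier: 2.80 × √0.637 = 2.24, so power is Φ(2.24 − 1.96) = 61%. Uniform: 2.80 × √0.75 = 2.43, power 68%.
- Tertiles, 2 df: noncentrality 2.80² × 0.793 = 6.2, power 60%. Uniform: 2.80² × 0.889 = 7.0, power 65%. Tertiles keep more information, but the second degree of freedom uses up the gain.

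**4. On the trial's scale.** Evaluable: 350 × 0.7 = 245. Residual SD after baseline adjustment: 6 × √(1 − 0.4²) = 5.50. SE of the change in effect per SD of modifier: 2 × 5.50 / √245 = 0.703.

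| Change in effect per SD | Continuous | Median split | Tertiles |
|---|---|---|---|
| 1 point, formula | 30% | 20% | 19% |
| 1 point, simulated | 30% | 21% | 20% |
| 1.5 points, formula | 57% | 40% | 38% |
| 1.5 points, simulated | 57% | 41% | 37% |
| 2 points, formula | 81% | 62% | 62% |
| 2 points, simulated | 80% | 60% | 60% |

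In simulation all three tests hold about 5% under the null.

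**5. Baseline-RMDQ strata under a random intercept.** Take a normal baseline split at the median, with no entry limit.
- Within a stratum the baseline variance is 36 × (1 − 2/π) = 13.1. The follow-up variance is 36 × (1 − 0.16 × 0.637) = 32.3.
- Covariance is 0.4 × 13.1 = 5.2 between baseline and follow-up, and 14.4 − 0.16 × 36 × 0.637 = 10.7 between follow-ups.
- A random intercept averages these: variance 25.9, covariance 7.07, correlation 0.273.
- It therefore takes the adjusted three-month variance as 25.9 × (1 − 0.273²) = 24.0. The actual value is 32.3 + 0.273² × 13.1 − 2 × 0.273 × 5.2 = 30.5.
- SE ratio √(24.0/30.5) = 0.89. Type I error 2Φ(−1.96 × 0.89) = 8%.

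Simulation of the difference between two strata, true effect equal in both:
- 250 complete, baseline limited to 6-24: mean SE 1.18 against empirical SD 1.42, ratio 0.83; type I error 10-11%, and 13% with tertiles. Stratum effects −1.98 to −2.01 for a true −2.0.
- 350 with 30% missing, limited to 6-24: 1.16 against 1.38, ratio 0.84; 9.9%. Without the limit: 1.23 against 1.43, ratio 0.86; 8.8%.
- About 246 evaluable: 1.18-1.24 against 1.36-1.40; 9%. Pairing the smaller values gives a ratio of 0.87.

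Remedies, same set-up: unstructured covariance with baseline still a response, 5.5%; baseline RMDQ as covariate, 5.3% for strata and about 5% for a continuous term.

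**The case against.** The text does not say that the tests use the groups. Strata for presentation beside a continuous interaction test would fit the same sentence. The main-trial SAP may fix the form, the definition of severity and the cut-points. This stands: the point rests on the natural reading, and a reader should not infer that cut-points were left open or chosen after seeing the data.

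A reader might take the loss to be a third of the information whatever the grouping. The documents give no number of groups, and a third fits only a median split of a roughly normal, linear modifier. If the true modification is a threshold, grouping could do as well or better.

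The effect sizes that show the clearest gain are large. A change of 2 points per SD means no benefit one SD below the mean and double the planned benefit one SD above it. At 1 point per SD, both forms are badly underpowered (30% against 21%). This stands too; the continuous test is better, not strong.

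A reader might also conclude that baseline-RMDQ strata cannot be analysed validly while baseline is a response. That is not so. The estimates are unbiased, and an unstructured covariance brings the error rate back to about 5.5%. The fault lies in the equal-variance structure, and the protocol does not say that its random effect is only an intercept. Pain intensity is an equally possible meaning of severity. For pain strata, at an assumed correlation of 0.5 with RMDQ, simulated type I error was 7.8%, partly because of the RMDQ entry limit.

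**Conclusion.** The concern holds as a cheap improvement to supplementary analyses.

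- **Loss of power: holds on the natural reading.** A test that would have 80% power falls to about 60% for a roughly normal modifier and to 65-68% for a uniform one. This assumes a linear modifier and two or three equal groups.
- **Inflated type I error: conditional.** It needs severity to mean baseline RMDQ and the random effect to be a plain intercept. Standard errors are then about 13-17% too small with the entry limit applied, and the interaction error rate is about 9-13% instead of 5%. Further assumptions are normal scores, equal correlation before the entry limit, and a baseline mean of 9 or 12 before truncation. A correlation of 0.6 gave the same inflation (10%).

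This point does not touch the primary comparison at three months. It does not show that the modifier analyses are biased: the stratum effects are unbiased, and only their precision is overstated.

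**What to change.** - Define LBP severity by naming the variable, and state any cut-points used for display.
- Test age and baseline severity as continuous group-by-modifier interactions on the three-month effect, in one model with all participants. Check non-linearity, for example with a spline or against the displayed strata.
- Keep strata for presentation only.
- If baseline RMDQ is the modifier, take the six-week and three-month RMDQ as responses, with baseline RMDQ as covariate and a group-by-baseline term. A continuous baseline modifier requires taking baseline out of the responses.
- If strata are displayed from the pooled-baseline model, fit an unstructured covariance within each stratum.

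The cost is a few sentences of plan wording and no new data. The one downside is the linearity assumption, which must be checked. According to Section 1 of the cost-effectiveness SAP, the main results and their SAP are already published. For this trial the change would therefore be a further analysis, labelled post hoc unless the main-trial SAP already provides for it.

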4.2. Secondary outcomes

The average and worst LBP intensity within the past week will be assessed by asking “Please indicate your average/worst low back pain level during the last week”, using an 11-point numerical rating scale (NRS) ranging from zero to 10. The NRS is a valid and commonly used outcome for measuring pain in adults [40, 49, 50]. Pain duration measures length of participants’ current back pain episode and total duration of time with LBP by asking “What is the length of time you have had low back pain during this episode?” with scoring ranging from less than 1 week to more than 12 weeks and “What is the total length of time that you have had low back trouble during the last 12 months?” with scoring ranging from 0 days to everyday. Measures of pain intensity and duration are recommended as a core set of outcomes for LBP trials [40]. Pain medication evaluates the frequency of non-prescription pain medication use for LBP by asking “How many days during the last week have you taken non-prescription pain medication for low back pain?”

The Fear-Avoidance Belief Questionnaire (FABQ) assesses participant’s beliefs about how physical activity and work affect their LBP [51]. The FABQ is a 5-item questionnaire, where the participants score their beliefs about their LBP on an ordinal scale ranging from zero [completely disagree] to six [completely agree]. The Pain Self-Efficacy Questionnaire (PSEQ) assesses the participant’s level of confidence in carrying out specific activities despite their pain [52, 53]. The PSEQ is a 10-item questionnaire scored on an ordinal scale ranging from zero [completely disagree] to six [completely agree].

Activity Limitation evaluates if LBP has limited work and leisure time activities. The questionnaire consists of two single items with response options “yes” and “no.” Work Ability is measured by a single-item and rated on an 11-point NRS scale ranging from zero [completely unable to work] to 10 [work ability at its best] [54].

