Self-reported physical activity is evaluated by a revised version of the Saltin-Grimby Physical Activity Level Scale, where participants indicate their amount of time per week performing leisure activities with four levels of intensity ranging from sedentary to vigorous physically active [55]. Function is evaluated by the Patient Specific Functional Scale (PSFS) where the participants, on up to two self-selected activities, are asked to rate if they are unable to do or are having difficulty with their ability to perform self-selected activities regarded as important by the participants themselves [56, 57]. The ability to carry out the activity/activities is rated from zero [unable to perform] to 10 [able to perform].

Sleep is assessed by self-report using four items concerning problems with falling asleep, waking up repeatedly, waking up too early, and feeling sleepy during the day [58]. Items are scored in three categories; [seldom or never], [sometimes] or [several times a week]. The information retrieved from these four items approximates the information necessary to diagnose insomnia according to the DSM-V criteria [59]. Stress is evaluated with the Perceived Stress Scale (PSS), a 10-item questionnaire asking about frequency of thoughts and feelings related to perceived stress [60]. Participants indicate their frequency of experiencing stress-related issues on a 5-point Likert scale, ranging from [never] to [very often].

Three outcome measures are included to assess general health and perception of illness. Health-related quality of life is evaluated with the EuroQoL 5-dimension (EQ-5D) questionnaire [61]. A 5-point Likert scale ranging from [no problems] to [complete inability] is used to assess the health-related quality of life within each of the five dimensions (i.e., mobility, self-care, activities, pain/discomfort and anxiety/depression). The Brief Illness Perception Questionnaire (BIPQ) [62] evaluates the participants’ illness perception in an 8-item questionnaire. Items are scored on an ordinal scale ranging from zero [no

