problems] to 10 [worst severity] [62]. The *Patient Health Questionnaire-8* (PHQ-8) is an 8-item questionnaire used to evaluate the participants' depressive symptoms [63]. Items are scored on a 4-point Likert scale scoring frequency of experiencing symptoms of depression [63]. Also, a single item question for *Patient's Global Perceived Effect* will be asked at all follow-ups, where participants are asked to rate improvement or deterioration of their LBP compared to before the intervention.

Participants randomised to the selfBACK DSS in addition to usual care are also asked a set of weekly tailoring questions used to individualise their self-management plan. The tailoring questions include items on pain (NRS for pain intensity [41]), function (item 5 from the Chronic Pain Grade Questionnaire [64]), kinesiophobia (1-item Tampa [65]), work ability (1-item WAI [54]), sleep (single item, modified from s-HUNT-Q [58]), pain self-efficacy (item 5 and 9 from PSEQ [66]), stress (4 items from PSS [60]), symptoms of depression (2 items from PHQ-8 [63]), and barriers for self-management (single item, customised to selfBACK). In total, this comprises 17 tailoring questions; however, participants will only be asked a maximum of 7 questions per week (most commonly 4 questions). The selection of the relevant questions is based on a set of rules implemented in the backend of the DSS, taking into account the progression of the self-management process and the individual participant characteristics.

5. Statistics

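### The secondary outcomes are assigned one linear mixed model with pooled baseline, which miscalibrates intervals for the yes/no items when prevalence changes and does not apply as written to Global Perceived Effect

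*Protocol*

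**What the plan says.** Protocol section 5.2 describes the primary analysis as a linear mixed model in which "individual participants will be specified as a random effect, accounting for the within subject covariance structure". Group and time enter as one joint variable: "Here, baseline levels are pooled over the two study groups assuming that any baseline differences are due to chance". For the rest it says: "Secondary outcomes will be analysed using a similar approach as described above for the primary outcome, with linear mixed models for repeated measures". It makes no exception by outcome type and names no logistic, ordinal or follow-up-only model.

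Protocol section 4.2 lists these among the secondary outcomes:

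- Activity Limitation: "The questionnaire consists of two single items with response options" yes and no.
- Sleep, four items: "Items are scored in three categories; [seldom or never], [sometimes] or [several times a week".
- Physical activity, reported with "four levels of intensity ranging from sedentary to vigorous physically active".
- Length of the current pain episode, "with scoring ranging from less than 1 week to more than 12 weeks".
- Global Perceived Effect, a single item that "will be asked at all follow-ups, where participants are asked to rate improvement or deterioration of their LBP compared to before the intervention".

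Section 4 opens by saying that all outcomes are collected at baseline as well as at each follow-up. That conflicts with the description of Global Perceived Effect.

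The supplied SAP covers cost-effectiveness only. Under its heading on effectiveness measures it refers back to the clinical trial protocol for the clinical endpoints.

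**The concern.** A linear mixed model with a participant random effect assumes the same total variance at every time point. The variance of a yes/no answer is p(1−p), so it moves with the proportion p. If nearly everyone reports a limitation at baseline and about half do at follow-up, the variance rises sharply. The model averages the small baseline variance into the follow-up standard error, which is then too small. If the variance falls instead, the standard error is too large. Section 5.2 judges precision by the 95% interval, so an interval with the wrong coverage misstates the evidence on that outcome.

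Global Perceived Effect raises a different problem. It has no baseline value, so a model built around a pooled baseline level cannot be applied to it as written, and the plan does not say what replaces it.

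For the ordered items the question is what a mean difference on a category code means to a reader.

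**Working it through.** **The plan's own figures.** The documents give no figure for the secondary-outcome model, so there is none to reproduce.

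**Inputs from the protocol.** 175 participants per arm and 30% dropout at three months (section 5.1); baseline, six weeks and three months in the model, participant random effect, pooled baseline (section 5.2).

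**Assumptions.** The proportions answering yes and the correlation between repeated answers (latent 0.5 or 0.6) are not in the documents.

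**Hand check, no treatment effect, no dropout, before any gain from the baseline value.**

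- Variance used by the model ≈ the average of p(1−p) over three time points: V = (V_base + 2·V_follow)/3.
- Model SE of a follow-up difference = √(2V/175). True SE = √(2·V_follow/175).
- False-positive rate = 2·[1 − Φ(1.96 × model SE / true SE)].

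| Yes at baseline → follow-up | V_base | V_follow | V | Model SE | True SE | False positives |
|---|---|---|---|---|---|---|
| 90% → 50% | 0.090 | 0.250 | 0.197 | 0.047 | 0.053 | 8.2% |
| 95% → 50% | 0.0475 | 0.250 | 0.1825 | 0.046 | 0.053 | 9.4% |
| 70% → 30% | 0.210 | 0.210 | 0.210 | 0.049 | 0.049 | 5.0% |
| 70% → 20% | 0.210 | 0.160 | 0.177 | 0.045 | 0.043 | 3.9% |

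For the first row: (0.09 + 0.25 + 0.25)/3 = 0.197; √(2 × 0.197/175) = 0.047; √(2 × 0.25/175) = 0.053.

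**Simulation of the full model** (random intercept, pooled baseline, 175 per arm, latent correlation 0.5). Several runs gave about 8 to 10% for 90% or 95% then 50%, with 11% the highest single result (95% case). They gave 5.1 to 5.6% for 70% then 30%, and about 3.5% for 70% then 20%. Participant-clustered robust standard errors gave about 5% throughout.

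**Simulation with dropout** (30% missing at three months, 15% at six weeks, completely at random; latent correlation 0.6), coverage of the nominal 95% interval for the three-month difference:

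| Outcome: baseline → three months (one arm / other arm) | Model-based | Robust |
|---|---|---|
| Yes/no: 97% → 50% / 50% | 87.6% | 95.4% |
| Yes/no: 90% → 50% / 40% | 91.1% | 95.4% |
| Yes/no: 60% → 20% / 10% | 98.2% | 94.6% |
| Three-category score | 95.9% | 95.6% |
| Four-level score | 94.7% | 94.4% |

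In the 90% case the model SE was about 14% too small. In the 60% case it was about 20% too large. Across all yes/no scenarios tried, coverage ran from 87% to 99%, and bias in the estimated difference was at most 0.003. The fault lies in the interval, not the estimate. The three- and four-level scores were simulated with modest shifts between categories; the pain-duration bands were not simulated.

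**Global Perceived Effect.** With baseline and two follow-ups, the joint group-and-time variable has 5 columns. With no baseline data its rank is 4. Dropping the baseline level gives 4 columns of rank 4, so a follow-up-only mixed model can be fitted.

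**The case against.** The strongest reply is that the harm depends on prevalences the documents do not give. That is right. A reader might infer that the yes/no intervals are too narrow in general. The documents do not support this: where the variance is unchanged or falls, the intervals are about right or too wide. High baseline limitation is plausible, because section 2.3 requires recent care-seeking and an RMDQ score of 6 or above. But one item concerns work, and section 2.3 does not require participants to be employed.

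A reader might also infer that the model cannot be fitted to Global Perceived Effect. That is too strong. Only the baseline term is not estimable, and the protocol promises a similar approach, not an identical model. A follow-up-only version fits that wording; the plan should say so.

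Nor does the variance argument carry over to the ordered items, where coverage was near nominal in the cases tried. What remains is interpretation of the mean, on which statisticians differ. The physical activity item may even be time reported at each intensity, since the scored variable is not defined.

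Finally, section 5.2 promises a main-trial SAP, and the administrative section of the cost-effectiveness SAP says it was published as a supplement. It was not supplied and may already assign models by outcome. The point is therefore about what the protocol specifies, not about whether the trial has such a plan.

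What survives is that the protocol states a rule, and following it for the yes/no items gives intervals whose coverage depends on how prevalence moves.

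**Conclusion.** The point holds in a limited form. As written, section 5.2 applies a constant-variance linear model to two yes/no items and a pooled-baseline model to an item with no baseline.

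For the yes/no items the consequence is miscalibration in either direction: too many false positives if the variance rises from baseline, and conservative intervals if it falls. The size rests wholly on assumed prevalences and on the assumed correlation. For Global Perceived Effect the defect is an unspecified adaptation, together with a contradiction between sections 4 and 4.2. For the ordered items no interval problem was shown.

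The change is worth making because it costs little. It concerns secondary outcomes only.

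**What to change.** In the protocol, or in the main-trial SAP if it does not already do so:

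- **Activity Limitation.** Keep the same mean model with participant-clustered robust standard errors, or use a GEE or mixed logistic model. Report marginal risk differences with 95% intervals.
- **Global Perceived Effect.** Use a model on follow-up data only, without a baseline term, adjusted for country and care provider. Reconcile section 4 with section 4.2 on whether this item is collected at baseline.
- **Sleep, physical activity and pain duration.** The linear mixed model may stay, with the coding and the meaning of a mean difference stated. Proportional-odds models or pre-set dichotomies are optional; the first adds an assumption and the second discards information.

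The cost is a short table of model and effect measure by outcome. The small downside is that effects may be reported on more than one scale. No extra data or participants are needed.
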